### **9.11 Visit windows and missed visits**

Visit windows are defined in HVTN 115 Study Specific Procedures. For a visit not performed within the window period, a Missed Visit form is completed. If the missed visit is one that required safety assessments or local safety labs, HVTN CRS staff should attempt to bring the participant in for an interim visit as soon as possible.

Procedures performed at an interim visit are usually toxicity/safety assessments (including local safety labs) and HIV testing. With the exception of HIV testing, these procedures are performed only if they were required at the missed visit or if clinically indicated. HIV testing may be performed as deemed appropriate by the study staff. Blood samples for immunogenicity assays are not typically collected at interim visits.

If a missed visit required vaccination, please refer to Section 7.3.2 and Section 7.3.3 for resolution.

## **9.12 Early termination visit**

In the event of early participant termination, site staff should consider if the following assessments are appropriate: a final physical examination, clinical laboratory tests (including urine dipstick, CBC with differential, and chemistry panel), pregnancy testing, social impact assessment, and HIV test.

## **9.13 Pregnancy**

If a participant becomes pregnant during the course of the study, no more injections of study product will be given, but remaining visits and study procedures should be completed unless medically contraindicated or applicable regulations require termination from the study. In case of required termination, enrollment in an observational study should be offered to the participant. If the participant terminates from the study prior to the pregnancy outcome, the site should make every effort to keep in touch with the participant in order to ascertain the pregnancy outcome. Pregnancies and pregnancy outcomes will be reported.

## 10 Laboratory

### 10.1 HVTN CRS laboratory procedures

The HVTN Site Lab Reference Manual provides further guidelines for operational issues concerning the clinical and processing laboratories. The manual includes guidelines for general specimen collection, special considerations for phlebotomy, specimen labeling, whole blood processing, HIV screening/diagnostic testing, and general screening and safety testing.

Tube types for blood collection are specified in Appendix I and Appendix J. For tests performed locally, the local lab may assign appropriate tube types.

In specific situations, the blood collection tubes may be redirected to another laboratory or may require study-specific processing techniques. In these cases, laboratory special instructions will be posted on the protocol-specific section of the HVTN website.

### 10.2 Total blood volume

Required blood volumes per visit are shown in Appendix I and Appendix J. Not shown is any additional blood volume that would be required if a safety lab needs to be repeated, or if a serum pregnancy test needs to be performed. The additional blood volume would likely be minimal. The total blood volume drawn for each participant will not exceed 500 mL in any 56-day (8-week) period.

### 10.3 Primary immunogenicity timepoints

#### Part A

The primary immunogenicity timepoint in Part A is at visit 8 (day 126) (ie, 2 weeks after the third vaccination visit). Endpoint assays for humoral and cellular responses are performed on participants at the primary immunogenicity timepoint and may be performed at baseline. Depending on the number of responders observed, assays for humoral and cellular responses may be performed on participants at other timepoints; the schedule is shown in Appendix I.

#### Part B

The primary immunogenicity timepoints in Part B are at visit 10 (day 238) (ie, 2 weeks after the fourth vaccination visit) and visit 15 (day 500) (2 weeks after the sixth vaccination visit). Endpoint assays for humoral and cellular responses are performed on participants at the primary immunogenicity timepoints and may be performed at baseline. Depending on the number of responders observed, assays for humoral and cellular responses may be performed on participants at other timepoints; the schedule is shown in Appendix J.

## 10.4 Endpoint assays: cellular

### 10.4.1 Flow cytometry

Flow cytometry will be used to examine vaccine-specific CD4+ and CD8+ T-cell responses following stimulation of PBMCs with synthetic HIV peptides that span the proteins encoded by the vaccine construct. ICS parameters will include cytokines such as IFN- $\gamma$ , IL-2, and TNF- $\alpha$ , and may include other cytokines to identify T cells of specific functionality (such as Th2 and Th17). Markers of cytotoxic potential (Granzyme B, perforin and CD57) may also be included. Data will be reported as percentages of CD4+ or CD8+ T cells responding to a specific peptide pool. Additional cell surface markers, cytokines, or functional markers may also be analyzed.

Flow cytometry will also be used to phenotypically characterize peripheral follicular helper T cells (pTfh). Identification of pTfh will be based on expression of CXCR5 and PD-1 on CD4+ T cells, and may include additional markers.

## 10.5 Endpoint assays: humoral

### 10.5.1 Binding antibody assays

HIV-1 Env binding IgG and IgA antibodies to the vaccine immunogens (EnvSeq-1 gp120 TF, 53, 78, 100) will be assessed on plasma/serum samples from study participants taken at the primary immunogenicity timepoints and baseline. Conformational epitopes (ie CD4BS specificities using differential binding to EnvSeq-1 gp120 compared to CH505 I $\Delta$ 371 protein and sCD4 blocking) will be determined. Specimens from other timepoints as well as other HIV antigens (ie other conformational epitopes and linear epitopes and profiling the antibody subclasses (IgG1, IgG2, IgG3, IgG4) may also be assayed based on the results of the initial assay.

### 10.5.2 Neutralizing antibody assay

HIV-1-specific neutralizing antibody assays will be performed on serum samples from all study participants taken at the primary immunogenicity timepoints. Specimens from the baseline and other timepoints may also be analyzed at the discretion of the HVTN Laboratory Program, which may be contingent on the results of the primary immunogenicity timepoints. Assays will be performed with the 4 EnvSeq-1 vaccine isolates (CH0505.TF, CH0505.w53.e16, CH0505.w78.33, CH0505.w100.B6) and a tier 1 variant of the TF strain, CH0505.wk4.3. Additional assays will test neutralization of heterologous tier 1 and tier 2 isolates [73].

### 10.5.3 B-cell lineage and repertoire analysis

Single memory B cells or plasmablasts will be single cell sorted. For plasmablasts, VH and VL genes will be amplified and cloned into an IgG1 backbone for expression and determination of binding and neutralization. For memory B cells, Env reactive memory B cells will be sorted using CH505 Env hooks, and then single cell sorted into individual wells of 96 well plates. VH and VL genes will be amplified and cloned into an IgG1 backbone and tested for Env binding and HIV neutralization. In some cases, memory B cells will be cultured in limiting dilution cultures and screened for binding and neutralization before PCR and VH and VL rescue. Finally, next generation sequencing

for all VH and VL families will be performed on memory B cells or plasmablasts for VH and VL genes.

## 10.6 Lab assay algorithm

The Lab Assay Algorithm lists assays to characterize cellular, humoral, and innate immune responses as well as host genetics that may be conducted to determine endpoints in HVTN vaccine trials. The type of assay(s) employed will be dependent on the response obtained by the primary immunogenicity assays at relevant timepoints. Please note that the Lab Assay Algorithm will be updated periodically to include new assays.

## 10.7 Exploratory studies

Samples may be used for other testing and research related to furthering the understanding of HIV immunology or vaccines. In addition, cryopreserved samples may be used to perform additional assays to support standardization and validation of existing or newly developed methods.

### 10.7.1 Fc-Mediated Antibody Effector Function

Additional assays to measure the induction of antibody Fc-mediated antibody functions (ie antibody dependent cellular cytotoxicity, phagocytosis, FcR binding, glycan modifications, recognition of virus particles and infected cells, etc.) may be performed on select samples and timepoints based on the primary analysis.

### 10.7.2 Microbiome analysis

Swabs of stool and/or bulk stool samples will be shipped to a central laboratory. Stool samples will be subjected to culture to obtain bacteria samples that are processed to yield a homogeneous stool flora lysate of each culture type. These lysates are then available to use to assess antibody binding by Western blot, ELISA, or other methods. In addition, stool samples will be subjected to chaotropic lysis and bead beating to liberate bacterial DNA, followed by DNA extraction. Purified DNA will be subjected to quality control qPCR assays to measure total bacterial load and assess for PCR inhibitors. Broad-range 16S rRNA PCR will be performed. Bacterial community composition will be assessed using taxonomic assignment of reads to a custom reference set of 16S rRNA gene sequences from the human gut. Some samples may be analyzed by shotgun metagenomics to create protein expression libraries to analyze the effect of stool composition on vaccine response. Finally, bulk stool samples will have antibodies extracted for analysis of the presence of mucosal antibodies elicited by the vaccine.

## 10.8 Other use of stored specimens

The HVTN stores specimens from all study participants indefinitely, unless a participant requests that specimens be destroyed or if required by IRB/EC, or RE.

Other use of specimens is defined as studies not covered by the protocol or the informed consent form for the main study (Appendix A).

This research may relate to HIV, vaccines, the immune system, and other diseases. This could include limited genetic testing and, potentially, genome-wide studies. This research is done only to the extent authorized in each study site's informed consent form, or as otherwise authorized under applicable law. Other testing on specimens will occur only after review and approval by the HVTN, the IRB/EC of the researcher requesting the specimens, and the CRS's IRBs/ECs/REs if required.

The protocol sample informed consent form is written so that the participant either explicitly allows or does not allow their samples to be used in other research when they sign the form. Participants who initially agree to other use of their samples may rescind their approval once they enter the study; such participants will remain in this study and their samples will only be used for the studies described in this protocol. If a participant decides against allowing other research using his or her samples, or at any time rescinds prior approval for such other use, the study site investigator or designee must notify HVTN Regulatory Affairs in writing. In either case, HVTN Regulatory Affairs directs the HVTN Lab Program not to use samples from these participants for such other uses.

CRSs must notify HVTN Regulatory Affairs if institutional or local governmental requirements pose a conflict with or impose restrictions on other use of specimens.

## **10.9 Biohazard containment**

As the transmission of HIV and other blood-borne pathogens can occur through contact with contaminated needles, blood, and blood products, appropriate precautions will be employed by all personnel in the drawing of blood and shipping and handling of all specimens for this study, as currently recommended by the CDC and the NIH or other applicable agencies.

All dangerous goods materials, including Biological Substances, Category A or Category B, must be transported according to instructions detailed in the International Air Transport Association Dangerous Goods Regulations.

## 11 Safety monitoring and safety review

### 11.1 Safety monitoring and oversight

#### 11.1.1 HVTN 115 PSRT

The HVTN 115 PSRT is composed of the following members:

- DAIDS medical officer representative,
- Protocol chair and cochair,
- Protocol Team leader,
- Core medical monitor, and
- Clinical safety specialist.

The clinician members of HVTN 115 PSRT are responsible for decisions related to participant safety.

The Protocol Team clinic coordinator, project manager, vaccine developer representative, clinical trial manager, and others may also be included in HVTN 115 PSRT meetings.

#### 11.1.2 HVTN SMB

The SMB is a multidisciplinary group consisting of biostatisticians, clinicians, and experts in HIV vaccine research that, collectively, has experience in the conduct and monitoring of vaccine trials. Members of the SMB are not directly affiliated with the protocols under review.

The SMB reviews safety data, unblinded as to treatment arm, approximately every 4 months. The reviews consist of evaluation of cumulative reactogenicity events, AE, laboratory safety data, and individual reports of adverse events requiring expedited reporting to DAIDS. To increase the sensitivity for detecting potential safety problems, the SMB will review safety data aggregated across multiple protocols that use the same or similar vaccine candidates. The SMB conducts additional special reviews at the request of the HVTN 115 PSRT.

Study sites will receive SMB summary minutes and are responsible for forwarding them to their IRB/EC and any applicable RE.

#### 11.1.3 SDMC roles and responsibilities in safety monitoring

The roles and responsibilities of the SDMC in relation to safety monitoring include:

- Maintaining a central database management system for HVTN clinical data;
- Providing reports of clinical data to appropriate groups such as the HVTN 115 PSRT and HVTN SMB (see Section 11.1.2);

#### 11.1.4 HVTN Core roles and responsibilities in safety monitoring

- Daily monitoring of clinical data for events that meet the safety pause and HVTN 115 PSRT AE review criteria (see Section 11.4);
- Notifying HVTN CRSs and other groups when safety pauses or planned holds are instituted and lifted (see Section 11.4);
- Querying HVTN CRSs for additional information regarding reported clinical data; and
- Providing support to the HVTN 115 PSRT.

### 11.2 Safety reporting

#### 11.2.1 Submission of safety forms to SDMC

Sites must submit all safety forms (eg, reactogenicity, adverse experience, urinalysis, local lab results, concomitant medications) before the end of the next business day after receiving the information. The forms should not be held in anticipation of additional information at a later date. If additional information is received at a later date, the forms should be updated and resubmitted before the end of the next business day after receiving the new information.

#### 11.2.2 AE reporting

An AE is any untoward medical occurrence in a clinical investigation participant administered a study product/procedure(s) and which does not necessarily have a causal relationship with this treatment. An AE can therefore be any unfavorable and unintended sign (including an abnormal laboratory finding), symptom, or disease temporally associated with the use of an investigational study product/procedure(s), whether or not related to the investigational study product/procedure(s). All AEs are graded according to the Division of AIDS Table for Grading the Severity of Adult and Pediatric Adverse Events, Version 2.0, November 2014, available on the RSC website at <http://rsc.tech-res.com/safetyandpharmacovigilance/gradingtables.aspx>, except:

- Weight loss is required to be reported as an AE only if it is considered to be deleterious to the participant's health (see *HVTN 115 Study Specific Procedures*);
- Injection Site Erythema or Redness and Injection Site Induration or Swelling will not consider interference with usual social and functional activities such that:
  - Grade 1 is: 2.5 to < 5 cm in diameter OR 6.25 to < 25 cm^2 surface area;
  - Grade 2 is: ≥ 5 to < 10 cm in diameter OR ≥ 25 to < 100 cm^2 surface area;
  - Grade 3 is: ≥ 10 cm in diameter OR ≥ 100 cm^2 surface area OR Ulceration OR Secondary infection OR Phlebitis OR Sterile abscess OR Drainage;
  - Grade 4 is: Potentially life-threatening consequences (eg, abscess, exfoliative dermatitis, necrosis involving dermis or deeper tissue);

- The grading of Insomnia events will consider the criteria within the Insomnia parameter as well as the general AE functional table such that:
  - Grade 1 Insomnia is defined as: Mild difficulty falling asleep, staying asleep, or waking up early causing no or minimal interference with usual social and functional activities with intervention not indicated;
  - Grade 2 Insomnia is defined as: Moderate difficulty falling asleep, staying asleep, or waking up early, causing greater than minimal interference with usual social and functional activities with intervention indicated;
  - Grade 3 Insomnia is defined as: Severe difficulty falling asleep, staying asleep, or waking up early, causing inability to perform usual social and functional activities with intervention or hospitalization indicated.

If a definition of insomnia falls between 2 grades, the final grading will be selected based on the degree of interference with usual social and functional activities caused by the symptoms.

All AEs are reported to the SDMC on the appropriate CRF. Clinic staff should evaluate every AE to determine if (1) the AE meets the requirements for expedited reporting to DAIDS (Section 11.2.3), (2) if the AE meets the criteria for a safety pause/prompt AE review (Section 11.4) and (3) if the AE is a potential immune-mediated disease that may be listed as an AE of special interest (AESI). A sample list of AESI is provided in Appendix M.

Sites are expected to notify the CSS of any serious safety concern requiring their attention (see Table 11-1). Telephone numbers and email addresses are listed in the Key Resource Guide of the HVTN 115 Study Specific Procedures. Telephone numbers and email addresses are found on the protocol home page on the HVTN Members' site (<https://members.hvtn.org/protocols/hvtn115>). Concerns requiring immediate attention should be communicated by calling the clinical safety phone.

In the case of email notification, the CSS will reply during working hours (US Pacific Time) to confirm that the email has been received and reviewed. If email service is not available, the HVTN CRS should notify the CSS of the event by telephone, then submit CRFs.

In addition, site investigators are required to submit AE information in accordance with IRB/EC and any applicable RE requirements.

### **11.2.3 Expedited reporting of adverse events to DAIDS**

Requirements, definitions and methods for expedited reporting of AEs are outlined in Version 2.0 (January 2010) of the *Manual for Expedited Reporting of Adverse Events* to DAIDS (DAIDS EAE Manual), which is available on the RSC website at <http://rsc.tech-res.com/safetyandpharmacovigilance/>. The SAE Reporting Category will be used for this study.

The internet-based DAIDS Adverse Experience Reporting System (DAERS) must be used for expedited AE reporting to DAIDS. In the event of system outages or technical difficulties, expedited AE reports may be submitted via the DAIDS EAE Form. For

questions about DAERS, please contact [[contact]](mailto:[contact]) or from within the DAERS application itself.

Sites where DAERS has not been implemented will submit expedited AE reports by documenting the information on the current DAIDS EAE Form. This form is available on the RSC website: <http://rsc.tech-res.com/safetyandpharmacovigilance/>. For questions about expedited AE reporting, please contact the RSC ([[contact]](mailto:[contact])).

The study products for which expedited reporting are required are

- CH505TF HIV gp120 with GLA-SE or placebo
- CH505w53 HIV gp120 with GLA-SE or placebo
- CH505w78 HIV gp120 with GLA-SE or placebo
- CH505w100 HIV gp120 with GLA-SE or placebo
- DNA Mosaic-Tre *env* or placebo

While the participant is in the main study reporting period (See Section 3), the SAE Reporting Category will be used.

After the protocol-defined AE reporting period for the study, unless otherwise noted, only Suspected, Unexpected Serious Adverse Reactions as defined in Version 2.0 of the DAIDS EAE Manual must be reported to DAIDS, if the study staff become aware of the events.

The NIAID/DAIDS will report all unexpected SAEs related to the study products observed in this clinical trial to the FDA in accordance with 21 CFR 312.32 (IND Safety Reports). However, because safety is a primary study endpoint, the Sponsor Medical Officer will not routinely be unblinded to study treatment assignment when there is an assessment of relatedness of the SAE with the study product(s); and the safety report will be sent to the FDA based on the blinded attribution assessment.

If the PSRT or sponsor believes unblinding of the site PI to treatment assignment will assist with the clinical management of the SAE, the PSRT will consult the independent HVTN SMB for a recommendation. In the event the HVTN SMB determines that unblinding is indicated, the SMB will inform the site physician of the participant's treatment assignment in such a manner as to maintain the study blind of the PSRT and study team. For additional impact and management of SAEs on the study, refer to Section 11.4.

## **11.3 Safety reviews**

### **11.3.1 Initial safety evaluation**

Enrollment across all participating HVTN CRSs will be restricted to a maximum of 1 participant per day and restricted to US sites until 10 participants have been enrolled. All

groups in Part A will enroll simultaneously. The HVTN 115 PSRT will review the cumulative safety data including at minimum local and systemic reactogenicity data reported for the first 72 hours postvaccination on each of these 10 participants, and will determine whether it is safe to proceed with full enrollment in Part A.

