#### 4.4 GLA-SE adjuvant

The IDRI GLA-SE adjuvant is a glucopyranosyl lipid adjuvant-stable emulsion (synthetic lipid A derivative mixed with squalene oil). The Clinical studies section outlines previous experience with GLA-SE and other antigens (see Section 4.9). This adjuvant, however, has not yet been administered to humans in combination with the EnvSeq-1 and the DNA Mosaic-Tre vaccines and therefore safety and tolerability of these products will be closely monitored.

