Test article-related microscopic findings were seen only at the injection sites for all terminal groups and all recovery groups and consisted of increased incidence and/or severity in all dosed groups compared to controls of a constellation of findings including: acute and chronic inflammation of the muscle; fibrosis; mixed cell infiltration/inflammation of the subcutaneous tissues; hemorrhage of the muscle and subcutaneous tissues; myofiber degeneration/necrosis; myofiber regeneration; and rare aggregates of vacuolated macrophages. While all groups had some degree of these findings, the DNA/CH505TF/GLA-SE-dosed group (Group 3), had the overall highest incidence and/or severity of hemorrhage, muscle inflammation (both chronic and acute), and myofiber degeneration/necrosis seen across terminal males and females at injection sites 1 and 2 combined. At injection sites 3 and 4 combined, Group 3 had the highest overall incidence and/or severity of the majority of the microscopic findings, including hemorrhage, edema, necrosis, vacuolated macrophages, muscle inflammation (both chronic and acute), subcutaneous infiltration/inflammation, and myofiber degeneration/necrosis and regeneration. Groups 2 and 4 were relatively similar to each other, with no clear trends in variation of incidence or severity of findings. At recovery, at all injection sites, there was a strong trend towards recovery in all groups, with generally reduced incidence and severity of most findings compared to terminal groups. Group 3 still had the highest overall incidence and/or severity of microscopic findings of vacuolated macrophages, chronic muscle inflammation, fibrosis, and subcutaneous infiltration/inflammation; with Group 2 and Group 4 being similar to each other and to Group 1 controls, albeit with slight increased incidence of vacuolated macrophages and, rarely, other findings consistent with resolving injection sites. The injection site findings were not considered to be adverse, given the generally low severity, lack of systemic findings, limited serum chemistry findings, and lack of associated clinical findings.

Mild, generally reversible and transient test article-related increases in monocytes, fibrinogen, globulin, and CRP and decreases in albumin and albumin/globulin ratio were observed after each dose administration in both sexes in all treatment groups. These changes were comparable in magnitude in all groups.

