### 11.3.2 Safety evaluation for moving from Part A to Part B

In addition to monitoring participant safety throughout the study period, the HVTN 115 PSRT will review all cumulative safety data available from groups 1 through 4 up to and including the 2-week visit after the third vaccination. Based on the assessment of this safety data, the HVTN 115 PSRT will make a decision regarding the appropriateness of moving to Part B from a safety perspective. The HVTN SMB may perform an additional unblinded review of this safety data to make the final determination based on safety for proceeding to part B.

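### The staged start and 72-hour review are tied to Part A only, so the first human use of DNA + gp120 + GLA-SE and of three new gp120s in Part B has no staged start of its own.

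*Combined protocol and SAP*

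**What the plan says.** Section 11.3.1 (Initial safety evaluation) has enrollment "restricted to a maximum of 1 participant per day and restricted to US sites until 10 participants have been enrolled". The PSRT then looks at cumulative safety data. The smallest set it must have is the "local and systemic reactogenicity data reported for the first 72 hours postvaccination on each of these 10 participants". The outcome of that review is a single decision, since the PSRT "will determine whether it is safe to proceed with full enrollment in Part A". No other decision is named, and nothing says that the count of 10 starts again for Part B.

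Section 11.3.2 governs the move to Part B. The PSRT is to "review all cumulative safety data available from groups 1 through 4 up to and including the 2-week visit after the third vaccination". SMB involvement is optional and uses the same data: "The HVTN SMB may perform an additional unblinded review of this safety data".

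The Table 3-1 schema and Section 4.5.1 show what is new in Part B. Part A gives CH505TF with GLA-SE, or placebo, as one injection per visit. Part B gives DNA Mosaic-Tre by Biojector into the same thigh as the protein and GLA-SE in Groups 6 and 8 from month 0. In Groups 5-8 it introduces w53 at month 2, w78 at month 4 and w100 at month 8. Groups 7 and 8 also receive two or three proteins mixed together.

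On prior human use, Section 4.4 says the adjuvant "has not yet been administered to humans in combination with the EnvSeq-1 and the DNA Mosaic-Tre vaccines and therefore safety and tolerability" will receive close attention. Section 4.9.1 says none of the four EnvSeq-1 proteins has been given to people. Section 4.7.1 reports that the rabbits given DNA, CH505TF and GLA-SE "had the overall highest incidence and/or severity of hemorrhage, muscle inflammation", among other injection-site findings.

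The duration entry in Section 3 allows time for planned holds. The only ones described anywhere are the two above.

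**The concern.** The protocol treats the first use of CH505TF/GLA-SE as a reason to enroll slowly and look early. On its own account, the DNA + protein + adjuvant combination and the three later proteins are equally untried in humans when Part B opens. The rabbit study also places the most marked local findings in the combination group. Yet the text neither repeats the staged start for Part B nor explains why it is unnecessary there.

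At stake is how many participants could receive the combination before anyone has deliberately reviewed the first recipients' early reactogenicity. This concerns limiting exposure. It does not affect any estimate or test in the analysis plan.

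**Working it through.** **1. Who is covered by each safety step.**

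| Step | Participants whose data are used | Given DNA + gp120 + GLA-SE | Given w53, w78 or w100 |
|---|---|---|---|
| 11.3.1 staged start | first 10, about 10 × 36/42 = 8.6 of them vaccinees | 0 | 0 |
| 11.3.2 gate to Part B | Groups 1-4, n = 42 | 0 | 0 |

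**2. Who is first exposed in Part B (Table 3-1).** DNA + CH505TF + GLA-SE at month 0: 20 + 20 = 40 of 90, or 44%. Each of w53, w78 and w100: up to 4 × 20 = 80. The other 40 vaccinees (Groups 5 and 7) receive CH505TF/GLA-SE at month 0, which Part A will already have tested. A month-0 stagger therefore bears on the DNA combination only. The new proteins arrive later.

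**3. The plan's own sensitivity figure.** Section 6.1.1 states that one Part B arm (n = 20) has a 90% chance of at least one event at a true rate of 10.9% or more. The formula is 1 − 0.1^(1/n). For n = 20 it gives 10.87%, which agrees. For the 40 combination recipients together it gives 1 − 0.1^(1/40) = 5.59%.

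**4. What 10 staged Part B participants would show.** This assumes the first 10 are a random draw from the planned 90 and ignores blocking.

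- Expected combination recipients: 10 × 40/90 = 4.4.
- Chance of none: C(50,10)/C(90,10) = 0.0018, or 0.2%.
- Chance of at least one event among them at true rate p: sum over k of [C(40,k) × C(50,10−k) / C(90,10)] × [1 − (1−p)^k].

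The rates below are assumptions, because the documents give none for the combination.

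| True rate p | At least one event among combination recipients in the first 10 | Among all 40 |
|---|---|---|
| 10% | 37% | 98.5% |
| 20% | 61% | >99.9% |
| 30% | 76% | >99.9% |

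**5. How many would be dosed before the first 72-hour data.** At r enrollments per day the number is 3r, of whom 3r × 40/90 = 1.33r would receive the combination. Under the 11.3.1 limit r is at most 1, giving 3. The documents state no r for Part B, so no figure follows.

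**6. Cost of repeating the procedure.** Ten enrollments at one per day take at least 10 enrollment days, or two weeks at five per week (assumed). Adding 3 days for the last participant's 72-hour data and time for the PSRT decision gives about two to three weeks in a 48-month study.

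**The case against.** The strongest reply is that Part B is already well watched. Participants are observed and assessed 25-60 minutes after injection (Section 9.3). Sites make contact within 72 hours, and reactions worse than mild are generally seen within 48 hours (9.10). Safety forms are due by the end of the next business day (11.2.1). HVTN Core reviews daily and the PSRT weekly (11.5). Table 11-1 imposes an immediate pause for a related Grade 4 or 5 SAE, and the PSRT may suspend vaccination before any rule is met (11.4). The SMB reviews unblinded data about every 4 months. All of this stands, and a reader who inferred that Part B opens without early safety review would be wrong. These measures are periodic or triggered by events, however, and none slows the first exposures. The Table 11-1 line for related Grade 3 or 4 AEs also leaves out subjective symptoms such as injection-site pain, which the 11.3.1 review would look at directly.

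The rabbit findings may tempt a reader to conclude that the combination is known to be harmful. Section 4.7.1 does not support that. The findings were judged not adverse, severity was generally low with a strong trend to recovery, and the animals received 20 mcg GLA-SE against 10 mcg here.

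Nor is Part A uninformative. It will have tested CH505TF/GLA-SE through three doses. DNA Mosaic-Tre by Biojector was given in HVTN 106, where pooled, blinded data showed no severe injection-site pain or tenderness (Table 4-6). GLA-SE at 10 mcg has been given to 48 people with other antigens. At month 0 only the co-administration is new.

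Part B is also unfinished by design. Doses are to be determined, and updated product and dose information goes to the FDA before it opens. That is a natural point at which to add the missing text. It is not human data on the combination.

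**Conclusion.** The gap is real but limited. The 11.3.1 staged start leads only to full enrollment in Part A, and the 11.3.2 gate rests only on Groups 1-4. No section provides a paced start or dedicated early review for the 40 participants first given DNA + gp120 + GLA-SE, or at first use of w53, w78 and w100 in up to 80. The sentence that sets the count of 10 does not itself name Part A. It is confined there because Part A enrolls first, the count is not reset, and only Part A's full enrollment is decided.

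A reader might assume a pace of, say, 2 to 8 per day and conclude that 6 to 24 people would be dosed before the first 72-hour data. The documents support no such range. The overall timeline does not imply a fast pace either: 48 months, less the 4.5 months to the Part A gate visit and 28 months of Part B follow-up, leaves 15.5 months for both enrollments, assays and the FDA submission. If Part B enrolls at about one per day or slower, the rate limit changes little, and the gain is mainly the defined review before full enrollment.

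The conclusion rests on the protocol text alone. The Study Specific Procedures were not available and may already address this.

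**What to change.** State in Section 11.3.1 or 11.3.2 that the existing 11.3.1 procedure is repeated for the first 10 Part B participants, with PSRT review of at least their 72-hour reactogenicity before full Part B enrollment. Say whether the US-site restriction is repeated too. Bring the planned holds in Section 3 and the close-monitoring statement in Section 4.4 into line with this. If the Study Specific Procedures already contain such a step, refer to it in the protocol.

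For w53, w78 and w100, have the existing weekly PSRT report (Section 11.5.2) flag the first recipients of each protein at months 2, 4 and 8. Separate checks without a hold at those visits would largely duplicate the weekly review and are not needed.

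The cost is protocol wording and about two to three weeks of slower accrual at the start of Part B. No visits or samples are added. The text should also say what the step can do: with about 4.4 combination recipients among the first 10, it limits early exposure to common or severe reactions and does not screen for rare ones.
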